9.4.4 SAFETY ANALYSES

AEs will be reported by frequency and percentage of participants presenting with the outcomes. Specific side effects and adverse events of interest are listed with secondary outcomes (9.4.3). All other side effects and adverse events outside of those listed in 9.4.3 will also be reported by frequency and percentage. Other AEs will be reported by severity of the adverse events (mild, moderate or severe) and related or not related to the study protocol. AEs will be grouped by Medical Dictionary for Regulatory Activity (MedDRA) System Organ Class (SOC).

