Follow up of medical management of EPL generally consists of confirmation of pregnancy expulsion by ultrasound examination or serial beta-hCG measurements in settings where ultrasound is not available [1]. There is no standard of care regarding specific intervals when ultrasonography or laboratory follow up assessment should take place. Study follow up schema for our study is based on participant follow up design from a similar study of mifepristone and misoprostol for EPL [2].

Participants will follow up with the UNC Family Planning Division for a transvaginal ultrasound on study day 3 to ensure expulsion of the gestational sac. Women generally experience cramping and vaginal bleeding 1 to 4 hours following misoprostol administration and pass their pregnancy within 24 hours of starting to bleed. Thus, follow up on day 3 will assess participants who are able to pass their pregnancy with a single dose of UPA and misoprostol.

For those who still have a pregnancy in the uterus, they will be offered an additional dose of 800mcg misoprostol, expectant management, or surgical management. Those who did not have expulsion of the pregnancy on day 3 and elect for an additional dose of misoprostol or expectant management will follow up with the UNC Family Planning Division for another transvaginal ultrasound on study day 8 to ensure expulsion of the gestational sac. As some studies of EPL assess for response 7 days after medication administration, we will be able to compare our data to similar studies through our day 8 follow up results [3]. Further, twenty-five to thirty percent of EPL will pass with expectant management alone one week after diagnosis [27].

Participants will be assessed for possible liver toxicity on study day 14 through a laboratory test of ALT, AST and total bilirubin.

All study participants will receive a phone call on study day 30 to what additional treatment patients needed for their early pregnancy loss, investigate any side effects or adverse events, and identify acceptability of the treatment. Most symptoms of bleeding and abdominal cramping following medical management of EPL occur in the first two to four weeks following medication administration; thus, 30 days is an adequate time to assess for side effects and acceptability of treatment while not being too remote from the time of the pregnancy passing.

A detailed description of all study visits is provided below:

Visit 1 (Day 0):

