9.2 SAMPLE SIZE RATIONALE

As this is a feasibility pilot study, no formal power calculation is required. We anticipate recruiting a convenience sample of 40 participants over the course of 12 months recruitment based on prior information from UNC Chapel Hill where approximately two patients with EPL are diagnosed per week at our two study locations after accounting for eligibility criteria and desire participation in the study. We estimate that of the approximately 100 patients diagnosed with EPL over the year, 40 patients will enroll given prior recruitment rates from studying mifepristone and misoprostol for early pregnancy loss (800 EPL patients for a total of 300 participants) [2].

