9.3 POPULATIONS FOR ANALYSES

As no randomization will take place in this analysis, all participants will be analyzed as part of the same population using univariate statistics. For the primary endpoint of feasibility, all patients screened for study participation will be included in the sample size. For the secondary endpoints of resolution of EPL, side effects/adverse events and patient acceptability, only participants adherent to study medication and completing all study visits will be analyzed. A sensitivity analysis will be conducted for the secondary endpoints that will include all participants enrolled in the study population for which data is available, regardless of adherence to study medication or completion of all study visits.

Patient disposition in the study will be reported, including the following:

- Number (%) of patients screened for study participation
- Number (%) of patients enrolled in study population
- Number (%) of participants adherent to study medication (UPA + misoprostol after 6 to 18 hours)
- Number (%) of participants non-adherent to study medication (any other route or timing of taking study medications)
- Number (%) of participants completing all study visits (day 0, day 3/8, day 30)

• Number (%) of participants completing some of study visits

Patient disposition will be reported as a flow chart and in tabular format in any future study communication and manuscript.

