9.4.9 EXPLORATORY ANALYSES

No additional exploratory analyses will be completed.

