10.1.2 STUDY DISCONTINUATION AND CLOSURE

This study may be temporarily suspended or prematurely terminated if there is sufficient reasonable cause. Written notification, documenting the reason for study suspension or termination, will be provided by the suspending or terminating party to study participants, investigator, the Investigational New Drug (IND) sponsor and regulatory authorities. If the study is prematurely terminated or suspended, the Principal Investigator (PI) will promptly inform study participants, the Institutional Review Board (IRB), and sponsor and will provide the reason(s) for the termination or suspension. Study participants will be contacted, as applicable, and be informed of changes to study visit schedule.

Circumstances that may warrant termination or suspension include, but are not limited to:

• Determination of unexpected, significant, or unacceptable risk to participants

- Demonstration of efficacy that would warrant stopping
- Insufficient compliance to protocol requirements
- Data that are not sufficiently complete and/or evaluable
- A life-threatening medical situation with determined study procedure causality
- Persistent or significant incapacity as a result of study drug(s) or procedure(s)
- A study participant with hepatic enzyme elevation greater than 3 times the upper limit of normal seen on laboratory testing on day 14

Study may resume once concerns about safety, protocol compliance, and data quality are addressed, and satisfy the sponsor, IRB and/or Food and Drug Administration (FDA).

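### Day 14 liver tests have no defined analysis, and the main side-effect/AE population can leave out exposed women, so an estimate of liver-test elevation is not guaranteed

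*Combined protocol and SAP*

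**What the plan says.** Section 4.1 gives the purpose of the tests: "Participants will be assessed for possible liver toxicity on study day 14 through a laboratory test of ALT, AST and total bilirubin". Section 2.3.1 names liver monitoring as the reason for the two study blood draws, and the Schedule of Activities places them at screening and Day 14.

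The results are used in several places:
- Exclusion 15 in section 5.2 requires all three tests to be at or below ULN at baseline.
- Section 8.2 follows elevated values, refers those that persist, and has the sponsor review the first 20 women before the next 20 enrol.
- Section 8.3.6 sends Hy's law cases to the FDA as expedited reports.
- Section 10.1.2 lists, as a circumstance that may warrant suspension, "A study participant with hepatic enzyme elevation greater than 3 times the upper limit of normal" at Day 14.

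The statistical section is silent on them. Section 9.4.3 lists nine named side effects plus a category for others, and two adverse events (transfusion for bleeding, and pelvic infection needing antibiotics). Section 9.4.4 says "Specific side effects and adverse events of interest are listed with secondary outcomes (9.4.3". It then adds that all other side effects and AEs will be reported by frequency and percentage.

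For the secondary endpoints, which it says include side effects and adverse events, section 9.3 states that "only participants adherent to study medication and completing all study visits will be analyzed". It adds a sensitivity analysis of all enrolled participants with data. Section 9.4.8 rules out individual listings, and 9.4.9 says "No additional exploratory analyses will be completed".

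**The concern.** The liver panel is the only laboratory test that the Schedule of Activities repeats after dosing. Because every woman enters at or below ULN, any later elevation is new since baseline and simple to count. The protocol describes this as the first use of UPA for this indication and intends the pilot to inform a larger trial. If no liver outcome is defined, that trial may inherit neither a rate nor an upper bound.

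The population adds to the problem. UPA is swallowed in front of study staff (section 6.4), so every woman dosed is exposed. Section 9.3 makes entry to the main analysis depend on what happens afterwards: when and how she takes misoprostol, and whether she attends every visit. Section 7.2 allows the investigator to withdraw a woman for an adverse event or a laboratory abnormality. A woman withdrawn for a raised liver test may not complete her visits, and would then drop out of the main analysis because of the event it should count.

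**Working it through.** **1. The plan's own figure.** The plan states no liver-related number. Its only sample-size figure is 40, from section 9.2: "We anticipate recruiting a convenience sample of 40 participants over the course of 12 months recruitment". It rests on recruitment ("We estimate that of the approximately 100 patients diagnosed with EPL over the year, 40 patients will enroll given prior recruitment rates"), not on power or precision ("As this is a feasibility pilot study, no formal power calculation is required"). Two patients a week for 52 weeks is 104, and 104 x 300/800 = 39.0. Using about 100 a year gives 100 x 300/800 = 37.5, or 38 rounded up. Both agree with 40 as a projection.

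**2. How a raised Day 14 result could reach the report.**
- As a named outcome: no. Sections 9.4.2 to 9.4.5 contain no ALT, AST or bilirubin variable, threshold, change from baseline or denominator.
- As an individual listing or a later exploratory table: no (9.4.8, 9.4.9).
- As an AE under the 9.4.4 catch-all: yes, if it is recorded as one. No section says that it must be. Section 8.2 says elevated values are followed, and 7.2 lists AE and laboratory abnormality as separate items.
- AE capture is not aimed at an asymptomatic result. The Schedule of Activities has AE review at screening, Day 3, Day 8 and Day 30, but none in the Day 14 column. Section 8.3.5 relies on self-report and on care the participant seeks. The Day 30 call solicits only bleeding and infection (8.3.4).
- The number tested is not planned anywhere. Complete attendance means Day 0, 3/8 and 30 (9.3, 9.4.2), so a missing Day 14 sample need not appear in the disposition table.

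**3. What a defined outcome would give.** With no events in n women, the exact two-sided 95% upper limit is 1 - 0.025^(1/n).

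| Women tested | Elevated | Exact 95% CI |
|---|---|---|
| 40 (all) | 0 | 0 to 8.8% |
| 40 (all) | 1 (2.5%) | 0.1% to 13.2% |
| 36 (assumes 90% of Day 14 samples obtained) | 0 | 0 to 9.7% |
| 20 (sponsor review) | 0 | 0 to 16.8% |

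The documents give no expected elevation rate. The chance of at least one event in 40 is 1 - (1 - p)^40. Over assumed true rates of 1%, 2%, 5% and 10%, this is 33%, 55%, 87% and 98.5%.

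**4. What the 9.3 restriction could cost.** Section 9.1 hypothesises adherence above 50% and retention above 90%. If both sat at those thresholds and were independent (an assumption), the adherent-completer set would be 40 x 0.5 x 0.9 = 18. No events in 18 gives an upper limit of 18.5%. If every woman were adherent and retained, the set would be 40 and the limit 8.8%. The loss of precision lies between these two. The possible bias from outcome-related withdrawal cannot be sized from the documents.

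**The case against.** The strongest reply is that the plan already has a route. The 9.4.4 catch-all covers every other AE, by severity and relatedness, and 9.4.1 attaches 95% confidence intervals to all statistics. The AE definition in 8.3.1 is broad, and 8.3.4 requires deterioration from the screening condition to be recorded. Since all baselines are normal, a clinically meaningful rise fits that wording. A reader might infer from the silence of 9.4.3 that no planned analysis can report a liver elevation. The documents do not support that: one recorded as an AE would be tabulated. What remains is that recording is left to judgement, and the catch-all supplies neither a number tested nor a ULN category.

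A reader might also infer that non-adherent or withdrawn women vanish from the analysis altogether. They do not, because 9.3 plans a sensitivity analysis of all enrolled women with data. The restriction is written for secondary endpoints, the section 3 table defines the AE outcome as self-report, and 9.4.4 states no restriction of its own. But 9.3 names adverse events, and 9.4.4 refers back to the secondary list without naming another population. The exposed population is therefore secondary at best.

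A third tempting reading is that a Day 14 elevation would show UPA liver toxicity. There is no comparison group (4.2), all women also take misoprostol and are given medication for pain and symptoms (6.1.2), and 6.5 plans no record of other concomitant medication. The elevation is new since baseline, no more.

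Liver safety is also not neglected in conduct: the sponsor review, the suspension ground, Hy's law reporting and the medical monitor all stand, and laboratory results enter the database (10.1.9.1). These are monitoring steps, however, and do not commit the trial to a reported result. It is fair, too, that the ban on exploratory analyses adds little, since a descriptive safety table is not exploratory.

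**Conclusion.** The point holds as a gap in prespecification and in the choice of safety population. The plan does not guarantee an estimate of liver-test elevation, although one could arise through AE recording. Its main side-effect/AE analysis can exclude women exposed to UPA, including any withdrawn because of an AE or laboratory abnormality.

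The information at stake is modest but usable: an upper limit of 8.8% if none of 40 women is elevated, and 16.8% if none of 20. These limits assume that every woman has a post-baseline result. The figure of 18.5% assumes an adherent-completer set of 18. The change should be made, because the data are already being collected and the trial already acts on them. It does not call the design or the monitoring rules into question.

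**What to change.** In section 9.4.4, make all participants given UPA the main safety population, regardless of adherence or visit completion, and align 9.3 with it. Add one liver-test table containing:
- the number with any post-baseline result and the number with the Day 14 sample missing;
- for ALT, AST and total bilirubin separately, n (%) above ULN and above 3 x ULN (the protocol's own levels), using any post-baseline value so that elevations found in the symptom-driven workups of 8.2 are counted;
- the number of Hy's law cases reported under 8.3.6;
- the median change from baseline to Day 14;
- exact 95% confidence intervals for the proportions.

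Use the same table at the 20-participant review. State in 8.2 or 8.3 whether a liver-test elevation is recorded as an AE. In the report, describe elevations as new since baseline, not as caused by UPA.

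The cost is one extra descriptive table from data already in the database. No added sampling is needed and no clinical rule changes.

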8.3.4 TIME PERIOD AND FREQUENCY FOR EVENT ASSESSMENT AND FOLLOW-UP

The occurrence of an adverse event (AE) or serious adverse event (SAE) may come to the attention of study personnel during study visits and interviews of a study participant presenting for medical care, or upon review by a study monitor.

All AEs including local and systemic reactions not meeting the criteria for SAEs will be captured on the appropriate case report form (CRF). Information to be collected includes event description, time of onset, clinician's assessment of severity, relationship to study product (assessed only by those with the training and authority to make a diagnosis), and time of resolution/stabilization of the event. All AEs occurring while on study must be documented appropriately regardless of relationship. All AEs will be followed to adequate resolution.

Any medical condition that is present at the time that the participant is screened will be considered as baseline and not reported as an AE. However, if the study participant's condition deteriorates at any time during the study, it will be recorded as an AE.

Changes in the severity of an AE will be documented to allow an assessment of the duration of the event at each level of severity to be performed. AEs characterized as intermittent require documentation of onset and duration of each episode.

The study sponsor will record all reportable events with start dates occurring any time after informed consent is obtained until 7 (for non-serious AEs) or 30 days (for SAEs) after the last day of study participation. At each study visit, the investigator will inquire about the occurrence of AE/SAEs since the last visit. Events will be followed for outcome information until resolution or stabilization.

All participants in the study will have notation on their UNC EPIC chart to alert the research staff if the patient is seen for any possible adverse event. Patients will be assessed for adverse events at their telephone follow up 30 days after study intervention. Solicited information on adverse events will include increased bleeding requiring hospital admission or blood transfusion and infection requiring hospital admission or IV antibiotics. All other adverse events will be identified based on unsolicited questioning during this telephone visit.

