9.4.3 ANALYSIS OF THE SECONDARY OUTCOME VARIABLE(S)

- Resolution of EPL
 - Binomial outcome: Absence of gestational sac on transvaginal ultrasound examination on Day 3 follow up
 - o Binomial outcome: Need for additional dose of misoprostol within 30 days of treatment
 - Binomial outcome: Need for uterine aspiration within 30 days of treatment
- Side Effects/Adverse Events
 - Side Effects Binomial Outcomes (N, %)
 - Fatigue
 - Headache
 - Dizziness or lightheadedness
 - Chills
 - Nausea
 - Diarrhea
 - Vomiting
 - Severe cramping
 - Fever
 - Other
 - Adverse Events Binomial Outcomes (N, %)
 - Excess bleeding requiring blood transfusion
 - Pelvic infection requiring antibiotics
- Patient Acceptability
 - Likert Scale Ordinal Outcomes (Median, Counts)

- Would you use this combination of medications again if you had another early pregnancy loss?
- Would you recommend this combination of medications to a friend with early pregnancy loss?
- If it was possible to take the first medication at home (versus in clinic), would you be more or less likely to use this combination of medications again?
- If it were possible to take the first medication at a different time (versus during your appointment), would you be more or less likely to use this combination of medications again?

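### Section 9.4.4 specifies severity and relatedness reporting only for adverse events outside the 9.4.3 list, so the eleven events named there are planned as N (%) only, although both items are required for all AEs

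*Combined protocol and SAP*

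**What the plan says.** Section 9.4.4 opens with a rule for every event: "AEs will be reported by frequency and percentage of participants presenting with the outcomes". It then points to 9.4.3 for the events of interest and turns to the remainder: "All other side effects and adverse events outside of those listed in 9.4.3 will also be reported by frequency and percentage". The next sentence gives the only rule on grading and attribution: "Other AEs will be reported by severity of the adverse events (mild, moderate or severe"), to which it adds a split by whether the event is judged related to the protocol. The section ends with MedDRA System Organ Class grouping for AEs in general.

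Section 9.4.3 sets the format for the named events. The side effects fall under a line beginning "Side Effects Binomial Outcomes (N" and the adverse events under one beginning "Adverse Events Binomial Outcomes (N"; each line continues with the percentage sign. The side effects are fatigue, headache, dizziness or lightheadedness, chills, nausea, diarrhea, vomiting, severe cramping and fever, plus a line for others. The adverse events are "Excess bleeding requiring blood transfusion" and pelvic infection treated with antibiotics.

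On collection, section 8.3.4 puts all AEs on the case report form, and the items recorded include the clinician's "assessment of severity, relationship to study product". Section 8.3.3.2 requires a relationship assessment for all AEs. Section 8.3.3.1 supplies the three-level severity scale. Section 9.4.8 states that data will be aggregated, with no individual listings.

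**The concern.** The protocol asks clinicians to grade and attribute every adverse event, but its analysis section specifies a use for those judgements only where the event is not on the 9.4.3 list. That list holds the symptoms the protocol itself expects: sections 2.3.1 and 8.3.5 name headache and nausea among the likely effects of ulipristal. Followed as written, the report would grade an unexpected, unlisted event and give only a count for the anticipated ones.

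Side effects and adverse events are a stated secondary objective (sections 1.1 and 3), and section 4.2 gives their evaluation as one reason for running this first study of the drug in early pregnancy loss. A count of women with nausea says less to those planning the next trial than the same count split into mild, moderate and severe. Severity also matters elsewhere in the protocol, since section 8.3.3.3 makes it one of the features that decide whether an event is expected.

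**Working it through.** The plan states no figure on this point, so the check compares what is required at collection with what is specified for reporting.

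**1. Does *Other* in 9.4.4 mean outside 9.4.3?** The sentence immediately before it uses the same word and defines it by reference to the 9.4.3 list. Nothing between the two sentences changes the meaning. The natural reading is yes.

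**2. Are severity or relatedness tables for the named events planned elsewhere?** Section 9.4.3 gives N (%) only. Section 9.4.1 sets general summary formats and does not mention grading. Section 9.4.9 plans no further analyses. Section 9.4.8 removes listings as a fallback. No section plans such tables.

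**3. Do the named side effects count as AEs for collection?** The definition in 8.3.1 covers any untoward medical occurrence, whether or not it is related. Section 8.3.5 says AE assessment includes symptoms possibly due to the medication and to the expulsion. So the rules in 8.3.3 and 8.3.4 reach them. This is an inference from those rules: the questionnaire items are not in the documents.

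**4. Which items lose what?**

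| 9.4.3 item | Threshold in the definition | Severity lost | Relatedness lost |
|---|---|---|---|
| Fatigue, headache, dizziness, chills, nausea, diarrhea, vomiting, fever (8) | No | Yes | Yes |
| Severe cramping (1) | Yes | Little | Yes |
| Bleeding with transfusion (1) | Yes | Little | Yes |
| Pelvic infection with antibiotics (1) | Yes | Little | Yes |

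Named items: 9 side effects + 2 adverse events = 11. Items for which lost grading matters: 11 − 3 = 8. Items without relatedness: 11.

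**5. What would relatedness add?** Under 8.3.3.2 a temporal relationship alone is enough to class an event as related. Section 6.1.1 defines the intervention as ulipristal followed by misoprostol, every participant receives it, and section 4.2 confirms there is no comparison group. The column would record the clinician's judgement on the regimen as a whole. It could not attribute a symptom to ulipristal rather than to misoprostol or the expulsion.

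**6. A wording mismatch.** Section 9.4.4 refers to relatedness to the study protocol, whereas 8.3.3.2 and 8.3.4 assess relationship to the study intervention or product.

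**The case against.** The strongest reply is that the plan is silent and does not prohibit anything. Section 9.4.4 begins and ends with rules for all AEs, and only one sentence between them says *Other*, which may be loose drafting. This stands in part. A reader might infer that the named events will go ungraded or that their grades may not be reported. The documents do not support that: the grades are required at collection, and nothing forbids tabulating them. What is missing is the specification. If the sponsor intends to grade everything, the text still needs the edit, because it now points the other way.

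The second reply is that the named symptoms are self-reported by questionnaire (sections 3 and 4.1), while 8.3.4 describes clinician-assessed events on a case report form, and several sections name side effects and adverse events separately. If the questionnaire records only yes or no and its answers are not carried to the AE form, the data for the fix would not exist. This stands as a condition. The Schedule of Activities places an AE review at each visit where the questionnaire is given (Days 3, 8 and 30), so the opportunity to grade is there, but the documents do not show the transfer.

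The third reply is that the secondary aims are hypothesis-generating only (sections 4.1 and 9.1), that incidence and acceptability are reported anyway, and that serious events have their own route in 8.3.6. This stands too, and it limits how much the gap matters.

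**Conclusion.** The point holds as a gap in specified safety reporting. Eleven named items are planned as N (%) only. Grading is materially lost for eight of them and relatedness is unreported for all eleven, although the protocol requires both for every AE. The effect is confined to descriptive safety reporting; recruitment, adherence, retention and the sample size are untouched.

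Two stronger readings are tempting and not supported. One is that the report could make no tolerability statement. It could, from symptom frequencies, the three items with a threshold built in, and the acceptability questions; the statement would only be less informative. The other is to size the loss by applying the headache and nausea rates in section 2.3.1 (18% and 12%) to 40 women. Those rates come from trials of the approved emergency-contraception use, not from 90 mg followed by misoprostol during a pregnancy loss. Nor is 40 the denominator of the main analysis: section 9.3 restricts it to adherent participants who completed all visits. The conclusion needs no such figure.

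It rests on two assumptions: that *Other* carries the meaning set by the preceding sentence, and that questionnaire symptoms fall under the all-AE collection rules.

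**What to change.** In 9.4.4, replace the sentence on *Other* AEs with wording to this effect: *All AEs, including every side effect and adverse event named in 9.4.3, will be tabulated by worst severity per participant and by relatedness to the study intervention, n (%).* Referring to the study intervention brings the section into line with 8.3.3.2. Deleting the word *Other* alone would not be enough, since it would neither set the per-participant rule nor make clear that questionnaire side effects are included.

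The reporting cost is extra columns in tables already planned. There is one operational step: confirm that symptoms reported on the questionnaire are entered on the AE form with the clinician's severity and relationship assessment, as 8.3.4 requires. If they are not, the form or the data-entry instruction needs a small change as well. When the relatedness column is reported, a footnote should say that it concerns the regimen as a whole and cannot separate ulipristal from misoprostol or the expulsion.
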